### **13.1. DERIVATIONS**

Duration of exposure (days) = (Date of last study medication administration – Date of first study medication administration) + 1.

## **14. STUDY MEDICATION COMPLIANCE**

Compliance to study medication is to be presented for the ITT population.

Compliance to study medication is to be summarised by descriptive statistics and treatment group for

- Compliance over first 4 doses (Visit 3A to Visit 3D)
- Compliance over last 4 doses (Visit 3E to Visit 3H)
- Overall compliance (Visit 3A to Visit 3H)

---

Document: TH005 SAP Version 2.docx

Author: [name]

Version Number:

2.0

Version Date:

24MAR2017

Template No: CS\_TP\_BS016 – Revision 3

Effective Date: 01May2012

Reference: CS\_WI\_BS005

Copyright © 2012 Quintiles Transnational Corp. All rights reserved.

The contents of this document are confidential and proprietary to Quintiles Transnational Corp. Unauthorized use, disclosure or reproduction is strictly prohibited.

---

## 14.1. DERIVATIONS

Compliance with double-blind study medication is to be calculated as the number of injections received (as indicated on the Study medication Administration eCRF (SDA1/2)) divided by the planned number of injections, expressed as a percentage, see calculations below:

- Compliance over first 4 doses = (Number of doses received from Visit 3A to Visit 3D / Planned number of doses [4]) X 100
- Compliance over last 4 doses = (Number of doses received from Visit 3E to Visit 3H / Planned number of doses [4]) X 100
- Overall compliance = (Total number of doses received / Planned number of doses [8]) X 100

Subjects are expected to receive one dose per visit from Visit 3A to Visit 3H for a total of 8 doses.

## 15. EFFICACY OUTCOMES

### 15.1. PRIMARY EFFICACY

#### 15.1.1. PRIMARY EFFICACY VARIABLE & DERIVATION

The primary efficacy analysis is to be performed for the ITT population and repeated for the PP population.

The primary efficacy variable is the mean of the daily combined score (CS) during the PAC3 period as recorded on each subject's eDiary.

The daily total rhinoconjunctivitis symptom score (TRSS) and the daily rescue medication score (RMS) are to be combined and a daily CS is to be calculated for each subject as follows:

- $CS = (TRSS / 8) + RMS$

For each subject the mean of the daily non-missing CS during the BAE, PAC1, PAC2 and PAC3 periods is to be calculated as follows:

- $\text{Sum(All CS in respective period)} / \text{Number of non-missing days in respective period}$

The TRSS is the sum of 8 individual TRSS symptom scores, namely runny nose, sneezing, blocked nose, itchy nose, itchy eyes, watery eyes, red eyes and itchy ear/palate. All symptoms are reflective over the previous 24 hours.

For each symptom, the subject is to rate (each morning) the severity as follows:

0 = absent

1 = mild, barely noticeable

2 = moderate, annoying/troublesome

3 = severe, very annoying/very troublesome

The TRSS is to have a range of 0 to 24. The TRSS on each day is to be calculated as follows:

TRSS = Runny Nose + Sneezing + Blocked Nose + Itchy Nose + Itchy Eyes + Watery Eyes + Red Eyes + Itchy Ear/Palate.

Rescue medications are to be provided to subjects to be used according to a pre-specified Rescue Medication Plan as specified in protocol Appendix 3: Rescue Medication Package Description and Rescue Medication Plan. The use of allergy rescue medications is to be scored based on Didier (Didier *et al*, 2009) as follows:

- RMS = 0; no allergy rescue medication used per day
- RMS = 0.5; at least one dose of antihistamine eye drops used per day
- RMS = 1; at least one dose of oral antihistamine used per day
- RMS = 2; at least one dose of intranasal corticosteroid used per day

---

Document: TH005 SAP Version 2.docx

Author: [name]

Version Number:

2.0

Version Date:

24MAR2017

Template No: CS\_TP\_BS016 – Revision 3

Effective Date: 01May2012

Reference: CS\_WI\_BS005

Copyright © 2012 Quintiles Transnational Corp. All rights reserved.

The contents of this document are confidential and proprietary to Quintiles Transnational Corp. Unauthorized use, disclosure or reproduction is strictly prohibited.

- RMS = 3; at least one dose of systemic corticosteroid used per day

The RMS score is not additive, the maximum value per day is used and therefore the maximum RMS per day is 3. The maximum CS per day is therefore 6.

The CS ranges from 0-6 and provides equal weighting (a maximum score of 3 each) for the contribution of the symptoms and for the rescue medication use.

If any of the 8 individual TRSS, namely sneezing, runny nose, blocked nose, itchy nose, itchy eyes, watery eyes, red eyes or itchy ear/palate for a given day is missing, the TRSS for that day is to be considered missing. If either the TRSS or the RMS is missing for a particular day then the CS is to be considered missing.

### **15.1.2. MISSING DATA METHODS FOR PRIMARY EFFICACY VARIABLE**

The primary analysis is to be performed using all available data on the assumption that the probability of missing observations is independent of unobserved measurements (missing at random). Therefore the missing values will not be imputed for the primary analysis.

A sensitivity analysis is to be performed to check the robustness of the primary results, assuming a missing not at random (MNAR) process. A pattern-mixture model based on control-based imputation is to be utilised for the sensitivity analysis.

The sensitivity analysis is described in Section 15.1.4 Sensitivity Analysis of Primary Efficacy Variable.

### **15.1.3. PRIMARY ANALYSIS OF PRIMARY EFFICACY VARIABLE**

The primary objective of this study is to test the hypothesis that there is no significant difference in adjusted mean CS between the active HDM-SPIRE treatment groups and placebo.

The null and alternative hypothesis is given by:

$$H_0: \mu_A = \mu_P$$

$$H_1: \mu_A \neq \mu_P$$

Where  $\mu_A$  is the adjusted mean for the active treatment groups and  $\mu_P$  is the adjusted mean for the placebo treatment group.

A point estimate and two-sided 95% confidence interval for the difference in adjusted mean between the active treatment groups and placebo is to be calculated using a Mixed Model Repeated Measures (MMRM) analysis for the PAC1, PAC2 and PAC3 period mean CS.

The MMRM is to include treatment, period and pooled region as main effects, gender, asthma status and Baseline CS as covariate, treatment-by-period and baseline-by-period interaction. An unstructured covariance matrix is to be used to assess within-subject dependence of the 3 observations (PAC1, PAC2 and PAC3) of mean CS per subject.

The following SAS® code is to be used:

---

Document: TH005 SAP Version 2.docx  
Author: [name]

Version Number: 2.0  
Version Date: 24MAR2017

Template No: CS\_TP\_BS016 – Revision 3  
Effective Date: 01May2012

Reference: CS\_WI\_BS005

**PROC MIXED data= IC INFO;**

```
CLASS subject treatment period pooled_region gender asthma_status;
MODEL CS=baseline treatment period pooled_region gender asthma_status treatment*period
baseline*period / DDFM=KR;
ESTIMATE '4 x 12 nmol HDM-SPIRE vs Placebo at PAC3' treatment 1 0 0 -1
treatment*period 0 0 1 0 0 0 0 0 0 0 -1 / CL;
REPEATED period / SUBJECT=subject TYPE=UN;
```

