## 3. STUDY DESIGN

### 3.1. GENERAL DESCRIPTION

This is a randomised, double-blind, placebo-controlled, parallel group, multi-centre field assessment of three dose regimens of HDM-SPIRE administered at 4 weekly intervals for 28 weeks.

Document: TH005 SAP Version 2.docx

Author: [name]

Version Number:

2.0

Version Date:

24MAR2017

Template No: CS\_TP\_BS016 – Revision 3

Effective Date: 01May2012

Reference: CS\_WI\_BS005

Copyright © 2012 Quintiles Transnational Corp. All rights reserved.

The contents of this document are confidential and proprietary to Quintiles Transnational Corp. Unauthorized use, disclosure or reproduction is strictly prohibited.

A total of approximately 660 subjects are to be randomised into the study, with approximately 165 subjects in each of the three HDM-SPIRE treatment groups and 165 in the placebo group.

Subjects are to attend the investigative centre for screening. Subjects meeting the inclusion/exclusion criteria are to be randomised to either one of the following three active treatment groups or the placebo group in a 1:1:1:1 ratio:

- 8 x placebo, 4 weeks apart (placebo)
- 4 x 12 nmol HDM-SPIRE followed by 4 x placebo, 4 weeks apart
- 4 x 20 nmol HDM-SPIRE followed by 4 x placebo, 4 weeks apart
- 8 x 12 nmol HDM-SPIRE 4 weeks apart

Following randomisation a total of 8 doses of HDM-SPIRE or placebo are to be administered at the investigative centre, one dose every 4 weeks ( $\pm 2$  days), for a total duration of 28 weeks as shown in the Table 1 below:

Table 1: Dosing Schedule								
Visit	3A	3B	3C	3D	3E	3F	3G	3H
Week ( $\pm 2$ days)	0	4	8	12	16	20	24	28
Treatment Group								
Placebo	P	P	P	P	P	P	P	P
HDM-SPIRE 4 x 12 nmol	X	X	X	X	P	P	P	P
HDM-SPIRE 4 x 20 nmol	X	X	X	X	P	P	P	P
HDM-SPIRE 8 x 12 nmol	X	X	X	X	X	X	X	X

X = HDM-SPIRE doses, P = Placebo doses.

Subjects are to complete an electronic diary (eDiary) during the following four periods for efficacy evaluation:

- Baseline allergy evaluation (BAE)

Subjects are to record Baseline Rhinoconjunctivitis symptom scores (RSS) and rescue medication score (RMS) in an eDiary during a period of approximately 3 weeks prior to randomisation.

The RSS and RMS assigned to the BAE period for a subject is to be taken as all scores entered on the subject's eDiary dated from the date of Visit 2A up to and including the date of Visit 2B.

- Post-administration collection period 1 (PAC1)

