## 7.4. MULTIPLE COMPARISONS/MULTIPLICITY

For the primary efficacy analysis a hierarchical (step-down) approach is to be used to control the overall Type I error rate at 5%.

For declaring statistical significance, a step-down approach ( first 4 x 12 nmol versus placebo, then 4 x 20 nmol versus placebo and then 8 x 12 nmol versus placebo) is to be used to control the overall Type I error at 0.05.

Thus:

- Step 1: If 4 x 12 nmol HDM-SPIRE versus placebo is significantly different at the 0.05 significance level, move to Step 2. If there is no statistical significance, no further statistical significance is to be declared
- Step 2: If 4 x 20 nmol HDM-SPIRE versus placebo is significantly different at the 0.05 significance level, move to Step 3. If there is no statistical significance, no further statistical significance is to be declared

---

Document: TH005 SAP Version 2.docx  
Author: [name]

Version Number: 2.0  
Version Date: 24MAR2017

Template No: CS\_TP\_BS016 – Revision 3  
Effective Date: 01May2012

Reference: CS\_WI\_BS005

Copyright © 2012 Quintiles Transnational Corp. All rights reserved.  
The contents of this document are confidential and proprietary to Quintiles Transnational Corp. Unauthorized use, disclosure or reproduction is strictly prohibited.

---

- Step 3: If  $8 \times 12$  nmol HDM-SPIRE versus placebo is significantly different at the 0.05 significance level, declare statistical significance.

Statistical significance is declared for each step individually if  $p < 0.05$  and overall statistical significance is to be declared if Step 1, Step 2 and Step 3 has  $p < 0.05$ .

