**RUN;**

Appropriate estimate statements are to be added for the contrasts of each HDM-SPIRE treatment group vs placebo for the PAC1, PAC2 and PAC3 periods.

- The treatment difference corresponding to the PAC3 period is to be utilised for the primary analysis
- The treatment difference corresponding to the PAC1 and PAC2 periods are to be utilised as exploratory analyses

Statistical significance is to be declared as set out in Section 7.4 Multiple Comparisons/Multiplicity.

Observed and change from Baseline values are to be summarised by descriptive statistics for the BAE, PAC1, PAC2 and PAC3 periods by treatment group.

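### The SAP's code for the primary contrast has 11 treatment-by-period coefficients where 12 are needed, so as printed it is not estimable

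*SAP*

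**What the plan says.** SAP Section 15.1.3 specifies a mixed model for repeated measures with treatment, period, pooled region, gender, asthma status, baseline, treatment-by-period and baseline-by-period. It introduces the program with "The following SAS® code is to be used", so the code is prescribed and not offered as an illustration. The one ESTIMATE statement written out begins "ESTIMATE '4 x 12 nmol HDM-SPIRE vs Placebo at PAC3' treatment 1 0 0 -1" and continues "treatment*period 0 0 1 0 0 0 0 0 0 0 -1 / CL".

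The text after the code makes PAC3 the primary time point: "The treatment difference corresponding to the PAC3 period is to be utilised for the primary analysis". The remaining contrasts are left to the programmer: "Appropriate estimate statements are to be added for the contrasts of each HDM-SPIRE treatment group vs placebo for the PAC1, PAC2 and PAC3 periods". SAP Section 7.4 places the 4 x 12 nmol comparison at the head of the hierarchy: "Step 1: If 4 x 12 nmol HDM-SPIRE versus placebo is significantly different at the 0.05 significance level, move to Step 2".

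**The concern.** The number of interaction coefficients does not match the number of treatment-by-period cells. Because the coefficients are read by position, one missing zero moves the final -1 back by one cell, to a different period. The statement then disagrees with its own label and with the sentence that makes PAC3 the primary contrast.

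The line is the written code for the test that gates the whole hierarchy. Followed exactly, it gives no estimate for that test. It is also the template for the other contrasts. The Section 15.1.3 analysis is reused for the 100 imputed datasets (15.1.4), the four alternative combined scores (15.1.5.3) and several secondary scores in 15.2.1, so a miscount copied from it would recur there.

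**Working it through.** **Inputs**

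- Treatment levels: 4. SAP 3.1 has subjects "randomised to either one of the following three active treatment groups or the placebo group in a 1:1:1:1 ratio".
- Period levels: 3. SAP 15.1.3 refers to the "dependence of the 3 observations (PAC1, PAC2 and PAC3) of mean CS per subject".
- Cell order: the CLASS statement lists treatment before period, so period varies fastest within treatment.
- Treatment order: the label and the main-effect coefficients put 4 x 12 nmol first (+1) and placebo fourth (-1). Sorting the output labels in SAP Appendix 1 alphabetically gives the same order: 4x12, 4x20, 8x12, Placebo.
- Assumption: the unfilled 12th coefficient is taken as 0.

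**Step 1: count and map**

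Cells needed: 4 x 3 = 12. Coefficients printed: 11.

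| Regimen | Cells | Printed (PAC1, PAC2, PAC3) | 12-coefficient line (PAC1, PAC2, PAC3) |
|---|---|---|---|
| 4 x 12 nmol | 1–3 | 0, 0, +1 | 0, 0, +1 |
| 4 x 20 nmol | 4–6 | 0, 0, 0 | 0, 0, 0 |
| 8 x 12 nmol | 7–9 | 0, 0, 0 | 0, 0, 0 |
| Placebo | 10–12 | 0, -1, 0 (unfilled) | 0, 0, -1 |
| Sum over treatments | | 0, -1, +1 | 0, 0, 0 |

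**Step 2: estimability by hand**

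Write a(t) for the treatment effects, g(p) for the period effects and d(t,p) for the interaction effects.

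- Printed contrast: a(4x12) - a(placebo) + d(4x12, PAC3) - d(placebo, PAC2).
- Labelled contrast: a(4x12) - a(placebo) + d(4x12, PAC3) - d(placebo, PAC3).

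Add any constant k to g(PAC3) and subtract k from d(t, PAC3) for all four treatments. Every fitted mean is unchanged. The printed contrast changes by -k, because only its first interaction term moves. The labelled contrast changes by -k + k = 0. A quantity that changes while every fitted mean stays the same is not estimable, so the printed contrast fails and the labelled one passes. This corresponds to the last row of the table: the printed period sums are 0, -1, +1 and the statement has no period term to match them.

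**Step 3: rank check**

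Columns of the over-parameterised design, with 8 pooled regions and 3 asthma levels as listed in SAP 7.1: intercept 1 + baseline 1 + treatment 4 + period 3 + region 8 + gender 2 + asthma 3 + treatment-by-period 12 + baseline-by-period 3 = 37.

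Rank: 1 + 1 + 3 + 2 + 7 + 1 + 2 + 6 + 2 = 25. A simulated data set of 660 subjects x 3 periods = 1,980 rows gives the same value.

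| Row added to the design | Rank | Estimable |
|---|---|---|
| None | 25 | – |
| Printed line | 26 | No |
| 12-coefficient line | 25 | Yes |
| Printed line plus period coefficients 0, -1, +1 | 25 | Yes |

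The last row confirms that the unmatched period sum is the cause. It does not give the labelled contrast, since it would compare 4 x 12 nmol at PAC3 with placebo at PAC2.

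**Step 4: can another reading rescue the line?**

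- If treatment varied fastest, cells 3 and 11 would be 8 x 12 nmol at PAC1 and at PAC3. That is not the labelled comparison either.
- Inserting one zero at each of the 12 possible places gives three distinct vectors. Before the +1 (3 places), the +1 moves to 4 x 20 nmol at PAC1 and the rank is 26. After the -1 (1 place), nothing moves and the rank is 26. Between the two (8 places), the result is the labelled contrast and the rank is 25.

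**Step 5: extent**

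Three regimens x three periods = 9 contrasts are required. One is written, so 9 - 1 = 8 remain. All nine, written with 12 coefficients, leave the rank at 25.

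**The case against.** The strongest objection is that this may not be an error in the SAP at all. The defect is a single missing zero in a run of identical zeros, in text read from a PDF by a program, and code elsewhere in the extracted SAP shows layout faults. No second copy of the line exists to compare. That stands: the original page decides, and if it shows 12 coefficients the point closes.

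The second objection is that nothing inferential is at risk. The label, the sentence naming PAC3, the hierarchy in SAP 7.4 and protocol Section 7.5.3.1.1 all state the same contrast. SAS would be expected to flag the line on its first run, and only one repair works. That also stands, and it limits the point to a code correction. It does not remove it, because the SAP says this code is to be used for the first confirmatory test and, followed exactly, it produces no estimate.

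Third, SAP 15.1.3 asks only for appropriate further statements and does not tell the programmer to copy this vector; a copied PAC3 line with the same slip would also be flagged. That is fair, and the knock-on risk is modest.

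Fourth, the figures of 37 columns and rank 25 depend on eight regions and three populated asthma levels. Region pooling is finalised at the blind data review, and the exclusion criteria may leave the third asthma level empty. With two asthma levels the design has 36 columns and rank 24, and the printed row still raises the rank by one. The conclusion does not depend on these counts.

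**Conclusion.** The point holds for the text as extracted. The size of the error is one coefficient in one ESTIMATE statement, which puts the -1 on placebo at PAC2 and makes the prescribed Step 1 contrast non-estimable. No wrong result is expected from it, and the sample size is unaffected.

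The cell mapping rests on placebo being the fourth treatment level. The non-estimability does not: with period varying fastest, the period sums are 0, -1, +1 whatever the order of the treatments. The remaining uncertainty is whether the zero is missing from the SAP itself or was lost in reading the PDF.

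**What to change.** 1. Compare the line with the original SAP page. If it has 12 interaction coefficients, no change is needed.
2. If it has 11, correct the interaction part before unblinding to `treatment*period 0 0 1 0 0 0 0 0 0 0 0 -1 / CL;`, that is, eight zeros between the +1 and the -1.
3. Write out the other eight contrasts, or at least confirm that each has 12 coefficients.
4. Optionally, state the treatment level order used in the analysis data set, because SAP Appendix 1 lists placebo first for outputs while the code treats it as last. Using LSMESTIMATE or LSMEANS differences with named levels would reduce the dependence on position.

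The cost is one zero in one line of code. The data, design, model and hypotheses do not change.

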**RUN;**

Appropriate estimate statements are to be added for the contrasts of each HDM-SPIRE treatment group vs placebo for the PAC1, PAC2 and PAC3 periods.

- The treatment difference corresponding to the PAC3 period is to be utilised for the primary analysis
- The treatment difference corresponding to the PAC1 and PAC2 periods are to be utilised as exploratory analyses

Statistical significance is to be declared as set out in Section 7.4 Multiple Comparisons/Multiplicity.

Observed and change from Baseline values are to be summarised by descriptive statistics for the BAE, PAC1, PAC2 and PAC3 periods by treatment group.

**15.1.4. SENSITIVITY ANALYSIS OF PRIMARY EFFICACY VARIABLE**

The sensitivity analysis is to be performed for the ITT population.

A pattern-mixture model based on non-ignorable missing observations, i.e. missing not at random (MNAR) is to be used where the conditional distribution of missing data, given the observed data, can be used to create multiple imputations for the missing values of subjects randomised to active treatment groups under the assumption that those subjects behave similar to those in the placebo treatment group after discontinuation, that is, the drug effect diminishes after subjects discontinue from the study. The approach is to be implemented by multiple imputations, where missing values are multiply replaced by sampling from the Bayesian posterior predictive distribution based on the model. The data is then analysed using the same primary analysis method as described in Section 15.1.3 Primary Analysis of Primary Efficacy Variable.

For imputation the following programming steps are to be performed using the SAS® procedures MI, MIXED and MIANALYZE:

Step 1) Impute non monotone missing data using the MCMC option of SAS PROC MI to obtain a monotone missing data pattern for all subjects

The following SAS code is to be used:

**PROC MI data= OUT=imp1 NIMPUTE=100 SEED=<seed>;****BY trtn;****MCMC CHAIN=multiple IMPUTE=monotone;****VAR BAE PAC1 PAC2 PAC3;****RUN;**

Document: TH005 SAP Version 2.docx

Author: [name]

Version Number:

2.0

Version Date:

24MAR2017

Template No: CS\_TP\_BS016 – Revision 3

Reference: CS\_WI\_BS005

Effective Date: 01May2012

Copyright © 2012 Quintiles Transnational Corp. All rights reserved.

The contents of this document are confidential and proprietary to Quintiles Transnational Corp. Unauthorized use, disclosure or reproduction is strictly prohibited.

Where **trtn** refers to the treatment group and BAE, PAC1, PAC2 and PAC3 refers to the mean score of each respective period.

The resulting output dataset **imp1** is to have 100 copies of the original dataset of subjects where each copy is to have a monotone missing pattern.

Step 2) The missing values for each pattern is to be imputed via the chained equation method, using SAS PROC MI option MONOTONE REG. The MNAR imputation is achieved by using only appropriate study data for each pattern. For example, to impute for period PAC3 assuming that the active arm missing data has the trajectory of placebo only placebo observations up to and including PAC3 is to be used.

The following SAS code is to be used:

```
PROC MI data=imp1 SEED=<> NIMPUTE=1 OUT=imp2;
  BY _Imputation_;
  CLASS trt;
  VAR BAE0 PAC1 PAC2 PAC3;
  MONOTONE REG;

  MNAR MODEL (PAC1 / MODELOBS =(trt='Placebo'));
  MNAR MODEL (PAC2 / MODELOBS =(trt='Placebo'));
  MNAR MODEL (PAC3 / MODELOBS =(trt='Placebo'));

RUN;
```

Step 3) Analyse the resulting dataset using the same method as described in Section 15.1.3 Primary Analysis of Primary Efficacy Variable for each of the 100 imputed datasets resulting in 100 estimates of the difference in adjusted mean CS between the active HDM-SPIRE treatment groups and placebo.

Step 4) An overall result is to be obtained by combining the estimates and using SAS PROC MIANALYZE to obtain the overall result.

The following SAS code is to be used:

```
PROC MIANALYZE data = imp2;
  MODELEFFECTS estimate;
  STDERR stderr;
  BY trt period;

RUN;
```

Where **estimate** refers to each estimate of the difference in adjusted mean CS between HDM-SPIRE and placebo and **stderr** refers to the standard error of each estimate.

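### The code prescribed for the only MNAR sensitivity analysis does not run as printed, and its imputation steps condition on fewer covariates than the primary model

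*SAP*

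**What the plan says.** Protocol 7.5 leaves the imputation method to the SAP. SAP 7.3 and 15.1.2 name one method, a control-based pattern-mixture model, and SAP 15.1.4 sets it out in four steps. Steps 1, 2 and 4 have printed SAS code, each block introduced as code that is to be used.

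- **Step 1** imputes within each arm (`BY trtn`) by MCMC until the missing pattern is monotone, with "VAR BAE PAC1 PAC2 PAC3", and writes 100 copies to `imp1`. The note beneath says that `trtn` "refers to the treatment group and BAE, PAC1, PAC2 and PAC3 refers to the mean score of each respective period".
- **Step 2** is "PROC MI data=imp1 SEED=<> NIMPUTE=1 OUT=imp2", run by `_Imputation_`, with "VAR BAE0 PAC1 PAC2 PAC3". Treatment is now called `trt`, and each PAC score is modelled from placebo observations.
- **Step 3** has no code. The primary method is applied to each imputed dataset, "resulting in 100 estimates of the difference in adjusted mean CS between the active HDM-SPIRE treatment groups and placebo". No output dataset is named.
- **Step 4** says in words that the estimates are combined. The code is "PROC MIANALYZE data = imp2", with model effect `estimate`, standard error `stderr`, and `BY trt period`. The note beneath defines `estimate` and `stderr` as the treatment difference and its standard error.

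For the analysis model, SAP 15.1.3 states: "The MMRM is to include treatment, period and pooled region as main effects, gender, asthma status and Baseline CS as covariate", with treatment-by-period and baseline-by-period terms. Asthma is also a randomisation stratum (Protocol 5.7).

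**The concern.** The SAP presents this code as the specification, so it should produce the analysis once its placeholders (input dataset, seed) are filled in. It does not. The Step 3 estimates have no dataset name and are not what Step 4 reads, and two variables change name between steps. Whoever programs the analysis has to settle the baseline name, the treatment name, the sort order, the reshape and the dataset to pool. If that happens after unblinding, the one MNAR check on all three regimen contrasts is no longer fully pre-specified.

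The covariates are a separate, statistical matter. The primary MMRM handles a missing PAC3 score conditionally on pooled region, gender and asthma status. The imputation handles it without them. A difference between the two results could therefore reflect a smaller conditioning set as well as the MNAR assumption.

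**Working it through.** **1. What each printed step needs and what it is given**

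| Step | Needs | Supplied by the printed steps | Not supplied |
|---|---|---|---|
| 2 | `_Imputation_`, `trt`, `BAE0`, `PAC1`–`PAC3` | `imp1`: `_Imputation_`, `trtn`, `BAE`, `PAC1`–`PAC3` | `trt`, `BAE0` |
| 4 | `estimate`, `stderr`, `trt`, `period` | `imp2`: completed scores, one column per period | `estimate`, `stderr`, `period` (and `trt`, unless it is in the input data) |

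The shape is also wrong. The pooling step needs one row per imputation for each contrast and period. With 3 regimens and 3 periods that is 3 × 3 = 9 groups of 100 rows, or 900 rows. `imp2` has one row per subject per imputation, about 660 × 100 = 66,000 rows at the planned enrolment.

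**2. Sort order**

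Step 1 writes `imp1` in `trtn` order and Step 2 reads it by `_Imputation_`, with no sort shown. The order matters because placebo and active subjects must fall in the same BY group. If the data were read unsorted, active-arm groups would contain no placebo observations to model from.

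**3. Covariates**

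- Primary MMRM: baseline, treatment, period, pooled region, gender, asthma status, treatment-by-period, baseline-by-period.
- Imputation models: baseline and PAC1–PAC3. Treatment enters through the BY statement in Step 1 and the placebo restriction in Step 2.
- In the MMRM but in neither VAR list: pooled region, gender, asthma status.

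**4. Likely size of the covariate omission**

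The point itself has no planned figure. For scale, the planning inputs in SAP 3.2 are a difference of 0.32, SD 0.986, two-sided 5% and 80% power:

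- n per group = 2 × (1.960 + 0.842)² × 0.986² / 0.32² ≈ 149.0, which rounds up to the plan's 150.
- Planned standard error = 0.986 × √(2/150) = 0.114.

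Protocol 7.2 expects up to 10% of subjects to drop out before PAC3 or have missing PAC3 data.

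Placebo-based imputation was simulated with and without one binary covariate in the imputation model. The assumptions are the reviewer's, not the plan's:

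- two arms of 165, 400 replicates, 10 imputations, and ANCOVA at PAC3 as a stand-in for the MMRM;
- covariate prevalence 40% and covariate effect 0, 0.3 or 0.6 CS units;
- active-arm missingness either unrelated to the covariate or concentrated in covariate-positive subjects. At 10% overall, the concentrated case is 17.5% against 5% (0.4 × 17.5% + 0.6 × 5% = 10%).

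Change in the estimated PAC3 difference (without the covariate minus with it):

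| Covariate effect | 10%, unrelated | 10%, concentrated | 20%, unrelated | 20%, concentrated |
|---|---|---|---|---|
| 0 | 0.0001 | 0.0003 | −0.0005 | 0.0007 |
| 0.3 | 0.0001 | −0.0028 | −0.0009 | −0.0053 |
| 0.6 | −0.0003 | −0.0057 | −0.0020 | −0.0112 |

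Standard errors were 0.114 at 10% missing and about 0.118 at 20%, almost unchanged by the covariate. The largest shift at 10% is 0.0057/0.32 = 1.8% of the planned difference, or 0.0057/0.114 = 0.05 standard errors. At 20% it is 0.0112/0.32 = 3.5%, or 0.0112/0.118 = 0.09 standard errors.

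**The case against.** The best defence is that the prose repairs the code. Step 3 yields 100 estimates, Step 4 combines them, and the closing note says what `estimate` and `stderr` are. Only the dataset label is wrong, and one correction is evident. A missing sort is programming housekeeping that an SAP would not normally print. The covariate effect is small. These points stand, and they limit the weight of the issue. They do not remove it: the SAP prescribes this code, and the naming, reshape and pooling structure are still unstated.

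A reader might go further in four ways that the documents do not support.

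- *The pooled sensitivity result would be wrong.* The variables that Step 4 asks for are absent from `imp2`, so the program would stop before reporting anything.
- *`BAE0` does not exist.* The contents of the input dataset are not listed and `imp1` carries copies of it, so a `BAE0` there cannot be excluded. What can be said is that the SAP does not define it and that it differs from Step 1.
- *The sensitivity analysis drops the primary covariates, so no shift could be attributed to the MNAR assumption.* Step 3 fits the full 15.1.3 model to every imputed dataset. Only the imputation conditions on less, and it still includes baseline. A shift of the size shown above would not obscure attribution at the planned missingness.
- *This is the only planned look at missing data.* The primary analysis is repeated in the per-protocol population, which is limited to subjects who completed all study visits (SAP 5.5 and 15.1.1). That is not an MNAR analysis, but it bears on dropout.

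**Conclusion.** The code for the only MNAR sensitivity analysis needs correction before it can be executed. Step 4 names the wrong dataset, and the baseline and treatment names are inconsistent between steps. This follows from the printed text and rests on no assumption beyond filling in the placeholders. The primary MMRM is unaffected.

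The omission of pooled region, gender and asthma status is a real but minor weakness. Under the simulation's assumptions its effect is at most about 0.006 CS units at 10% missing and about 0.011 at 20%. That simulation varied one covariate in a two-arm setting. It does not bound the joint effect of all three, or the effect under heavier or more selective dropout. The case for change is that the covariates are already collected, the correction is cheap, and the sensitivity analysis would then condition more nearly on what the primary analysis does.

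**What to change.** Amend SAP 15.1.4 before unblinding:

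1. Use one baseline name and one treatment name in all four steps.
2. Leave Step 1 without covariate dummies. It is a by-arm multivariate-normal MCMC, and sparse levels could make the within-arm covariance singular. SAP 7.1 lists eight pooled regions, and SAP 7.2 triggers pooling only below 5 subjects in total, so a region of 5 averages 5/4 = 1.25 per arm. The partly/uncontrolled asthma level should be nearly empty under exclusion criterion 5.
3. Sort `imp1` by `_Imputation_` before Step 2, so that each BY group holds placebo and active subjects together.
4. Add pooled region, gender and asthma status to the CLASS and VAR statements of the Step 2 monotone regression. Collapse levels with too few placebo subjects to estimate.
5. Reshape `imp2` to one row per subject and period, and run the 15.1.3 MMRM by `_Imputation_`. Save the ESTIMATE output (estimate, standard error, contrast, period, `_Imputation_`) as a named dataset.
6. Run PROC MIANALYZE on that dataset by contrast and period.

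The cost is a few more lines of code and some collapsing of sparse covariate levels. No new data are needed.
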